#### **Secondary objective**

- Change in basal insulin dose per unit body weight (U/Kg/day)
- Immunogenicity: incidence and change from baseline in the relative levels of ADA, incidence and change from baseline in the relative levels of anti-HCP antibodies.
- Rate of hypoglycemic events per 30 days; and occurrence of hypoglycemia

- Occurrence of local reactions, systemic reactions and other adverse events
- Change in fasting plasma glucose
- Change in 8-point SMBG profile
- Device-related safety assessments

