### ***7.3.2. Antibodies against Host Cell Protein Antibodies (anti-HCP)***

The multi-tiered sample analysis approach for immunogenicity testing will also be employed for the detection of antibodies directed against host cell proteins present in the drug product. In keeping with the multi-tiered sample analysis recommendations for immunogenicity testing, the assay design employed screening (no inhibition), confirmatory (competitive inhibition with excess HCP), and titer tiers. However, since a high positive rate of pre-existing antibodies is anticipated due to ubiquitous exposure of the general population to yeast proteins, sample analysis is limited to the screening and confirmatory tiers. Relative anti-HCP antibody levels over time will be estimated using sample ECL response in the screening assay.

The assay employed for anti-HCP antibody evaluation will be fully validated using a surrogate positive control antibody, developed from host cell protein antigens (*Pichia pastoris*). Host antigens for the reference product (from the host *Escherichia coli* K12) are not available to develop a parallel assay for Lantus anti-HCP antibodies. In order to maintain blinded analysis, both treatment arms will be evaluated with the assay. Any change in the sample analysis method will be mentioned in the sample analysis plan.

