### **9.2 General Considerations**

Statistical analysis of this trial will be the responsibility of Mylan or designated clinical contract organizations.

Any change to the data analysis methods will be mentioned in the statistical analysis plan. Any additional analysis, and the justification for making the change, will be described in the clinical study report. Additional exploratory analyses of the data will be conducted as deemed appropriate.

For the statistical analysis, baseline is visit 1, which includes the post study measurements of the main study MYL-GAI-3001.

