### ***9.9.2. Immunogenicity Profiles Analyses***

Continuous immunogenicity variables such as cross-reacting antibodies percent binding will be analyzed using the MMRM ANCOVA model, similar to the primary and secondary efficacy analyses. The model will include the fixed, categorical effect of region and

sequence group, visit, sequence group-by-visit interaction and the other as fixed effect terms region, and baseline value as covariates. The p-value for sequence difference and 95% confidence interval will be constructed. If the normal distribution assumption is severely violated, then non-parametric analysis will be performed using Wilcoxon rank-sum test for sequence comparison.

Descriptive statistical summaries for actual measurements and change from baseline will be displayed by visit for each sequence group. For categorical variables such as ADA positive and negative, frequency table will be presented by visit for each period for each sequence. Fisher's exact test will be used for sequence comparison by visit.

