17.6.2. IMMUNOGENICITY PROFILES ANALYSES

Following parameters will be summarized for immunogenicity.

- Total Insulin Antibodies
 - Percent Binding (%B/T, Continuous outcome)
 - Positive/Negative (Categorical outcome)
- Cross Reactive Insulin Antibodies
 - Percent Binding (%B/T, Continuous outcome)
 - Positive/Negative (Categorical outcome)

Document:	\\JEEDC-NAS01A\Biosdata\Mylan\INSULIN_GLARGINE\UXA25824\Biostatistics\Documentation\SAP	Version Number:	Final V1.0
Author:	[name] and [name]	Version Date:	[27JUL2016]

Template No: CS_TP_BS016 – Revision 3
 Effective Date: 01May2012

Reference: CS_WI_BS005

Copyright © 2012 Quintiles Transnational Corp. All rights reserved.

The contents of this document are confidential and proprietary to Quintiles Transnational Corp. Unauthorized use, disclosure or reproduction is strictly prohibited.

- Insulin(Drug) Specific Antibody
 - Percent Binding (%B/T, Continuous outcome)
- Anti-HCP
 - Positive/Negative (Categorical outcome)

Immunogenicity profiles with continuous variables (% binding) will be analyzed using the MMRM method for each assay, similar to change from baseline efficacy analyses. The model will include the terms region, treatment sequence group, visit, treatment sequence group-by-visit as fixed effects, and baseline value as covariate. The treatment sequence group difference and 95% confidence intervals will be constructed using the model at scheduled visits. In case the normal distribution assumption is severely violated, then non-parametric analysis will be performed using Wilcoxon rank-sum test for treatment sequence group comparison, Hodges Lehmann's estimator will be used to compute the median difference between the treatment sequence groups and the corresponding 95% confidence interval. Safety population will be used for ADA continuous variables. Immunogenicity profiles with dichotomous outcomes will be summarized with frequency and percentage at scheduled visits for each assay. Treatment sequence group comparison will be performed using Fisher's exact test. P-value for the two-sided test will be presented.

Correlation analyses of insulin cross-reactive antibodies with clinical factors such as HbA1c and insulin doses will be performed by treatment sequence group along with graphics to explore relationship of insulin antibodies with such factors for each assay method used. Additionally, mean (\pm SD) and median (IQR) for actual measurements by visit will also be presented.

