Regression plots will be produced to assess the consistency of results obtained between the two assay types, and the regression plots will be produced for Total Insulin Antibody, Cross Reactive Insulin Antibody and Insulin (Drug) Specific Antibody by treatment sequence group.

The incidence of patients with increase over 10% cross reacting antibody increase in both assays, of HbA1c over 0.2% increase and insulin dose increase at any visit will also be summarized descriptively (for categorical measures) together to explore treatment sequence group difference.

An individual data listing will be provided for the patients with increase over 10% cross reacting antibody increase in both assays, of HbA1c over 0.2% increase and insulin dose increase at Week 12, 24 and 36.

The observed and Change values of HbA1c, Insulin dose, Cross reactive antibodies (Both assays) Fasting blood glucose, Subject's age, Duration of diabetes and Adverse events reported will be presented in the listing.

Presence of anti-HCP antibodies in samples from patients will be assessed using a validated immunoassay method. The results will be presented as positive or negative from anti-HCP antibodies based on the samples that HCP assay was done. Frequency and percentage of presence of anti-HCP antibodies will be presented at scheduled visits by treatment sequence group. The p-value from Fisher's exact test will be presented to test the difference between the treatment sequence groups for scheduled visits.

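### Change in anti-HCP antibody level is a secondary objective, but the SAP analyses anti-HCP only as positive or negative

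*SAP*

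**What the plan says.** Protocol 2.1 sets two anti-HCP aims under immunogenicity: "incidence and change from baseline in the relative levels of anti-HCP antibodies". SAP 2.2, item 2, repeats both, so the SAP did not set out to drop the second.

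Protocol 7.3.2 says how level is to be measured: "Relative anti-HCP antibody levels over time will be estimated using sample ECL response in the screening assay". It also says that "sample analysis is limited to the screening and confirmatory tiers", so there will be no titer. The reason it gives is prior exposure: "since a high positive rate of pre-existing antibodies is anticipated due to ubiquitous exposure of the general population to yeast proteins". ECL is therefore the only level measure the trial has.

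For the analysis, Protocol 9.9.2 is general: "Continuous immunogenicity variables such as cross-reacting antibodies percent binding will be analyzed using the MMRM ANCOVA model". SAP 17.6.2 is narrower: "Immunogenicity profiles with continuous variables (% binding) will be analyzed using the MMRM method for each assay". Its parameter list gives total and cross-reactive insulin antibodies both a continuous and a categorical outcome, and drug-specific antibody a continuous one. Anti-HCP has a categorical outcome only. The closing text of the section confirms this: "The results will be presented as positive or negative from anti-HCP antibodies based on the samples that HCP assay was done", followed by frequencies, percentages and Fisher's exact test at scheduled visits.

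Protocol 9.2 states: "Any change to the data analysis methods will be mentioned in the statistical analysis plan". SAP 3.3 lists a wording correction to the primary endpoint and added sensitivity analyses, and nothing on anti-HCP. SAP 18, on data not summarized, is marked as not applicable.

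**The concern.** The SAP restates an objective with two parts and then provides an analysis for one of them. Positivity by visit answers the incidence part. Nothing answers the change-in-level part, not even a descriptive summary.

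Positivity is a poor substitute here. The test product is made in *Pichia pastoris*, the anti-HCP assay is built on proteins from that host, and repeated switching is what the trial studies. The protocol itself expects high pre-existing positivity from ordinary exposure to yeast. Movement from negative to positive would still show in the by-visit tables. A rise in a patient who was positive at baseline would not.

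**Working it through.** **Text comparison.** The claim is about consistency between documents, so there is no stated figure to reproduce.

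| Step | Anti-HCP incidence | Anti-HCP level |
|---|---|---|
| Objective (Protocol 2.1, SAP 2.2) | stated | stated |
| Measure (Protocol 7.3.2) | screening and confirmatory tiers | screening-assay ECL |
| Outcome variable (SAP 17.6.2) | positive/negative | none |
| Analysis (SAP 17.6.2) | frequency, percentage, Fisher by visit | none |
| Declared change (SAP 3.3) | not needed | none |

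The continuous model in SAP 17.6.2 cannot be stretched to cover ECL. Percent binding is the insulin-antibody radioimmunoassay measure, and ECL does not appear anywhere in the SAP.

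**Size.** The documents give no ECL standard deviation and no anti-HCP positivity rate, so the figures below rest on stated assumptions. Arm size is 69 (Protocol 9.1), or 62 after the 10% allowance (0.9 × 69 = 62.1).

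*(a) Ceiling on the binary test; no SD needed.* Assume k baseline-negative patients in each arm, no positive patient reverting, and every negative converting in one arm and none in the other. Two-sided Fisher then compares n/n with (n−k)/n; because the arms are equal, p = 2·C(n,k)/C(2n,k).

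| n per arm | k=5 | k=6 |
|---|---|---|
| 69 | 69/69 vs 64/69, p=0.0580 | p=0.0279 |
| 62 | 62/62 vs 57/62, p=0.0575 | p=0.0275 |

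So if baseline positivity is at least 64/69 = 93% (57/62 = 92% with 62 per arm), no single visit can reach p<0.05 under these conditions. Below that positivity the ceiling does not apply.

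*(b) Precision of a level comparison.* In SD units of log ECL, with baseline-to-visit correlation ρ and 69 per arm, SE = √[(2/69)(1−ρ²)]. The half-width is t(0.975, 134) × SE = 1.978 × SE. The shift with 80% power is (1.978 + 0.842) × SE.

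| ρ (assumed) | SE | 95% CI half-width | Shift with 80% power |
|---|---|---|---|
| 0.5 | 0.147 | 0.29 SD | 0.42 SD |
| 0.7 | 0.122 | 0.24 SD | 0.34 SD |
| 0.9 | 0.074 | 0.15 SD | 0.21 SD |

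*(c) Illustrative power at one visit.* Simulation with 69 per arm, 4000 replicates per cell, and the cut-off set to give the stated baseline positivity. The level doubles (log10 2) in one arm, only in patients positive at baseline. Each entry is Fisher power / baseline-adjusted log-ECL ANCOVA power.

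| log10 SD between/within patient (assumed) | 50% positive | 70% positive | 90% positive |
|---|---|---|---|
| 0.3/0.15 | 15% / 98% | 17% / >99% | 8% / >99% |
| 0.5/0.25 | 11% / 73% | 12% / 94% | 7% / >99% |
| 0.8/0.5 | 8% / 27% | 7% / 46% | 5% / 69% |

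With no effect and 70% positivity, rejection is 3–4% for Fisher and 4.5–5% for ANCOVA. Fisher exceeds its null rate in the table only because fewer positives fall back below the cut-off through assay noise.

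If instead the level doubles in every patient of one arm, Fisher does better where SDs and positivity are low: 97% against >99% at SDs 0.3/0.15 and 50% positivity. At 0.8/0.5 and 90% it is 9% against 76%.

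**The case against.** Five points can be made for the plan.

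- **Undeclared change.** Protocol section 9 never names an anti-HCP level analysis, and 9.9.2 reaches ECL only if its example is read broadly. The SAP's silence is then an incomplete plan rather than a clear breach of Protocol 9.2. That is fair. The finding does not need 9.2, SAP 3.3 or SAP 18: the objective, Protocol 7.3.2 and SAP 17.6.2 are enough.
- **Estimate, not test.** Protocol 7.3.2 promises estimation of levels over time, so a descriptive ECL summary by visit and sequence group would satisfy it. This also stands, and it makes the model a recommendation rather than an obligation. But the SAP has no descriptive summary either.
- **Assumptions in (c).** Confining the rise to patients already positive leaves Fisher little to detect. With doubling in everyone and 70% positivity, Fisher has about 91% power at SDs 0.3/0.15 and 53% at 0.5/0.25, against >99% for log ECL in both. The gap depends on who responds as well as on the SDs. These figures illustrate the loss; they do not measure it.
- **The sample analysis plan.** That plan was not available. Protocol 7.3.2 assigns it changes in the laboratory method, not the statistical analysis.
- **Data availability.** The SAP speaks only of samples on which the HCP assay was done, so how many ECL values exist, and whether they reach the analysis database, is not known from the documents.

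None of this supplies the missing analysis.

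**Conclusion.** The concern holds. The SAP carries the anti-HCP level objective forward, ignores the only measure the protocol provides for it, and plans a binary analysis that cannot show a rise in patients positive at baseline.

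That conclusion rests on the text alone. Its practical size depends on baseline positivity, ECL variability and which patients respond, none of which the documents give. In every scenario computed the level comparison has more power than the binary one, but the gain ranges from about 3 percentage points to more than 90.

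The scope is limited to one component of one secondary immunogenicity objective. The HbA1c equivalence analysis and the insulin-antibody analyses are not affected. It should be corrected before database lock.

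**What to change.** In SAP 17.6.2, add anti-HCP log ECL response from the screening assay as a continuous outcome in the model already specified there: region, sequence group, visit and sequence-by-visit as fixed effects, baseline log ECL as covariate, safety population, and the same Wilcoxon and Hodges-Lehmann fallback. Report descriptive statistics and the sequence difference with its 95% CI at scheduled visits. Keep the positivity tables for the incidence part. Record the addition in SAP 3.3.

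Baseline ECL comes from MYL-GAI-3001 (Protocol Table 4, footnote 3), so first confirm that those values are on the same scale as the extension-study values. A shift common to both arms would leave the group difference intact but make within-arm change uninterpretable. Whether any shift is common to both arms has to be checked with the laboratory, because the documents do not describe run layout or normalisation.

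If ECL values prove unusable, the consistent alternative is to remove the level component from the objective in both documents and say so in SAP 3.3. That leaves the question unanswered.

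The cost is SAP wording, one more model, a few tables and the scale check. The screening assay already yields ECL, so no new samples are needed. It adds one more secondary comparison without multiplicity adjustment, to be read descriptively.

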17.6.3. HYPOGLYCEMIA ANALYSES

Hypoglycemia is a state produced by a lower than normal level of glucose in the blood. Hypoglycemia is classified as severe, documented symptomatic, asymptomatic, probable symptomatic, relative, or nocturnal hypoglycemia. The details of Classification can be found in protocol Sections 7.4.8 and 7.5.6.1.

Document:	\\JEEDC-NAS01A\Biosdata\Mylan\INSULIN_GLARGINE\UXA25824\Biostatistics\Documentation\SAP		
Author:	[name] and [name]	Version Number:	Final V1.0
		Version Date:	[27JUL2016]

Template No: CS_TP_BS016 – Revision 3
Effective Date: 01May2012

Reference: CS_WI_BS005

Copyright © 2012 Quintiles Transnational Corp. All rights reserved.

The contents of this document are confidential and proprietary to Quintiles Transnational Corp. Unauthorized use, disclosure or reproduction is strictly prohibited.

Patients will be instructed to record all hypoglycemic events in the patient diary from visit 2 until the EOT visit. The hypoglycemic events will be reviewed by the investigator and transcribed into the eCRF by the investigator or designee after the diary has been collected.

Hypoglycemia rate per patient per 30 days calculated between two visits is defined as total number of episodes between two visits divided by the number of days between the visits, multiplied by 30 days. This rate will also be calculated per patient for nocturnal hypoglycemia episodes.

Hypoglycemia rate per patient per 30 days will be analyzed at all scheduled visit using MMRM method similar to the continuous efficacy variables at scheduled visits. The model will include the terms region, treatment sequence group, visit, visit-by-treatment sequence group as fixed effects, and baseline value as covariates. The rate per patient per 30 days calculated between two visits is defined as total number of episodes between two visits divided by the number of days between the visits, multiplied by 30 days. This rate will also be calculated per patient for nocturnal hypoglycemia episodes. In case the normal distribution assumption is severely violated, then non-parametric analysis will be performed using Wilcoxon rank-sum test for treatment sequence group comparison, Hodges Lehmann's estimator will be used to compute the median difference between the treatment sequence groups and the corresponding 95% confidence interval.

Due to the uneven visit intervals for scheduled visits, additional exploratory analyses for hypoglycemia rate per patient per 30 days based only on the SMBG week (during the week the SMBG is done) for each visit will be performed using same method as above.

The similar analysis will be done for asymptomatic hypoglycemia rate separately based only on SMBG week and none SMBG week.

For change from baseline of hypoglycemia rate, for graphical display at scheduled visits, LS means and 95% CI will be generated from the MMRM model. Additionally, mean (\pm SD) and median (IQR) for actual measurements by visit will also be presented.

The incidence of hypoglycemic episodes during a time period on treatment is defined as the incidence of patients with at least one hypoglycemic episode occurring within that period of time. Incidence of hypoglycemic episodes will be presented by treatment sequence group, visit and overall. Incidence of hypoglycemic episodes will also be summarized by category (Severe Hypoglycemia, Documented Symptomatic Hypoglycemia, Asymptomatic Hypoglycemia, Probable Symptomatic Hypoglycemia, Relative Hypoglycemia and Nocturnal Hypoglycemia). The detailed definition of each type of hypoglycemic event is mentioned in the protocol Section 7.5.6.1.

In addition, nocturnal hypoglycemia rate and incidence will be analyzed in a same way as overall hypoglycemic episodes

Listings of hypoglycemic episodes and severe hypoglycemic episodes will be presented by visit for each patient. If a sufficient number of severe hypoglycemic episodes are reported, then incidence summaries similar to the incidence of hypoglycemic episodes will be included.

18. DATA NOT SUMMARIZED OR PRESENTED

Not Applicable

Document:	\\JEEDC-NAS01A\Biosdata\Mylan\INSULIN_GLARGINE\UXA25824\Biostatistics\Documentation\SAP	Version Number:	Final V1.0
Author:	[name] and [name]	Version Date:	[27JUL2016]

Template No: CS_TP_BS016 – Revision 3
Effective Date: 01May2012

Reference: CS_WI_BS005

Copyright © 2012 Quintiles Transnational Corp. All rights reserved.

The contents of this document are confidential and proprietary to Quintiles Transnational Corp. Unauthorized use, disclosure or reproduction is strictly prohibited.

APPENDIX 1. PARTIAL DATE CONVENTIONS

Imputed dates will NOT be presented in the listings.

ALGORITHM FOR TREATMENT EMERGENCE OF ADVERSE EVENTS:

START DATE	STOP DATE	ACTION
Known	Known	If start date < study med start date, then not TEAE If start date >= study med start date, then TEAE
	Partial	If start date < study med start date, then not TEAE If start date >= study med start date, then TEAE
	Missing	If start date < study med start date, then not TEAE If start date >= study med start date, then TEAE
Partial, but known components show that it cannot be on or after study med start date	Known	Not TEAE
	Partial	Not TEAE
	Missing	Not TEAE
Partial, could be on or after study med start date	Known	If stop date < study med start date, then not TEAE If stop date >= study med start date, then TEAE
	Partial	Impute stop date as latest possible date (i.e. last day of month if day unknown or 31st December if day and month are unknown), then: If stop date < study med start date, then not TEAE If stop date >= study med start date, then TEAE
	Missing	Assumed TEAE
Missing	Known	If stop date < study med start date, then not TEAE If stop date >= study med start date, then TEAE

Document: \\JEEDC-NAS01A\Biosdata\Mylan\INSULIN_GLARGINE\UXA25824\Biostatistics\Documentation\SAP
 Author: [name] and [name] Version Number: Final V1.0
 Version Date: [27JUL2016]

Template No: CS_TP_BS016 – Revision 3
 Effective Date: 01May2012

Reference: CS_WI_BS005

Copyright © 2012 Quintiles Transnational Corp. All rights reserved.

The contents of this document are confidential and proprietary to Quintiles Transnational Corp. Unauthorized use, disclosure or reproduction is strictly prohibited.

START DATE	STOP DATE	ACTION
	Partial	Impute stop date as latest possible date (i.e. last day of month if day unknown or 31st December if day and month are unknown), then: If stop date < study med start date, then not TEAE If stop date >= study med start date, then TEAE
	Missing	Assumed TEAE

ALGORITHM FOR PRIOR / CONCOMITANT MEDICATIONS:

START DATE	STOP DATE	ACTION
Known	Known	If stop date < study med start date, assign as prior If stop date >= study med start date and start date <= end of treatment, assign as concomitant If stop date >= study med start date and start date > end of treatment, assign as post study
	Partial	Impute stop date as latest possible date (i.e. last day of month if day unknown or 31 st December if day and month are unknown), then: If stop date < study med start date, assign as prior If stop date >= study med start date and start date <= end of treatment, assign as concomitant If stop date >= study med start date and start date > end of treatment, assign as post treatment
	Missing	If stop date is missing could never be assumed a prior medication If start date <= end of treatment, assign as concomitant If start date > end of treatment, assign as post treatment
Partial	Known	Impute start date as earliest possible date (i.e. first day of month if day unknown or 1 st January if day and month are unknown), then: If stop date < study med start date, assign as prior If stop date >= study med start date and start date <= end of treatment, assign as concomitant If stop date >= study med start date and start date > end of treatment, assign as post treatment

Document:	\\JEEDC-NAS01A\Biosdata\Mylan\INSULIN_GLARGINE\UXA25824\Biostatistics\Documentation\SAP		
Author:	[name] and [name]	Version Number:	Final V1.0
		Version Date:	[27JUL2016]

 Template No: CS_TP_BS016 – Revision 3
 Effective Date: 01May2012

Reference: CS_WI_BS005

START DATE	STOP DATE	ACTION
	Partial	
Impute start date as earliest possible date (i.e. first day of month if day unknown or 1st January if day and month are unknown) and impute stop date as latest possible date (i.e. last day of month if day unknown or 31st December if day and month are unknown), then:
 
If stop date < study med start date, assign as prior
 
If stop date >= study med start date and start date <= end of treatment, assign as concomitant
 
If stop date >= study med start date and start date > end of treatment, assign as post treatment

	Missing	
Impute start date as earliest possible date (i.e. first day of month if day unknown or 1st January if day and month are unknown), then:
 
If stop date is missing could never be assumed a prior medication
 
If start date <= end of treatment, assign as concomitant
 
If start date > end of treatment, assign as post treatment

Missing	Known	
If stop date < study med start date, assign as prior
 
If stop date >= study med start date, assign as concomitant
 
Cannot be assigned as 'post treatment'

	Partial	
Impute stop date as latest possible date (i.e. last day of month if day unknown or 31st December if day and month are unknown), then:
 
If stop date < study med start date, assign as prior
 
If stop date >= study med start date, assign as concomitant
 
Cannot be assigned as 'post treatment'

	Missing	Assign as concomitant

Document: \\IEEDC-NAS01A\Biosdata\Mylan\INSULIN_GLARGINE\UXA25824\Biostatistics\Documentation\SAP
Author: [name] and [name] Version Number: Final V1.0
Version Date: [27JUL2016]

Template No: CS_TP_BS016 – Revision 3
Effective Date: 01May2012

Reference: CS_WI_BS005

Copyright © 2012 Quintiles Transnational Corp. All rights reserved.

The contents of this document are confidential and proprietary to Quintiles Transnational Corp. Unauthorized use, disclosure or reproduction is strictly prohibited.

